4.2.3.5 Supportive secondary safety endpoints

- Number of treatment emergent adverse events (AEs) during 16 weeks after randomisation
- Number of treatment emergent infusion site reactions during 16 weeks after randomisation
- Number of treatment emergent hypoglycaemic episodes classified both according to the American Diabetes Association definition and Novo Nordisk definition during 16 weeks after randomisation:
 - Overall
 - Daytime and nocturnal hypoglycaemic episodes (00:01-05:59 inclusive)
 - Hypoglycaemic episodes from start of meal until 1, 2, 4 hours and from 2 hours (exclusive) to 4 hours (inclusive) after start of meal
- Number of unexplained episodes of hyperglycaemia (confirmed by SMPG) during 16 weeks after randomisation
- Change from baseline 16 weeks after randomisation in clinical evaluations:
 - Physical examination
 - Electrocardiogram (ECG)
 - Vital signs (blood pressure, pulse)
 - Fundus photography/fundoscopy
- Change from baseline 16 weeks after randomisation in central laboratory assessments:
 - Haematology (haemoglobin, haematocrit, erythrocytes, thrombocytes, and leucocytes)
 - Biochemistry (total protein, creatinine, alanine aminotransferase (ALT), aspartate aminotransferase (AST), alkaline phosphatase (AP), sodium, potassium, albumin, and total bilirubin)
 - Urinalysis (for blood, protein, and ketones)
- Change from baseline 16 weeks after randomisation in body weight and body mass index (BMI)
- Number of change-of-infusion-sets per week during 16 weeks after randomisation
- Number of Subjects with at least one non-routine change-of-infusion-sets categorised by reasons for change-of-infusion-sets during 16 weeks after randomisation

5 Trial design

5.1 Type of trial

This is a double-blind, randomised, multicentre, multinational, active controlled, treat-to-target, parallel group trial with a 4-week run-in and a 16-week treatment period comparing the effect and safety of CSII of faster-acting insulin aspart vs. NovoRapid® in adult Subjects with T1DM. Subjects entering the trial will stay on their own insulin pump.

Protocol		Date:	04 February 2016	Novo Nordisk
Trial ID: NN1218-3854	CONFIDENTIAL	Version:	4.0	
UTN: U1111-1118-2480	CONFIDENTIAL	Status:	Final	

Page:

[figure not shown]
28 of 149

The total duration of the trial is approximately 26 weeks split into the following periods (see Figure 5–1):

• \leq 2-week for screening period

EudraCT no.: 2010-024054-11

- A 4-week run-in period primarily for reinforcement of Subject training in trial procedures, diabetes education and collecting baseline assessments
- A 16-week double-blinded treatment period
- A 7-day and 30-day follow-up period

Note: Prior to randomisation and after end of treatment Subjects are on marketed product.

Baseline is defined as randomisation.

Figure 5–1 Trial design

The trial includes a screening visit (Visit 1) to assess Subjects' eligibility and additional weekly visits/phone contacts during the trial. All Subjects eligible for the trial will at Visit 2 enter the 4-week run-in period, and they will continue on their currently prescribed insulin treatment. During the run-in period the Investigator will focus on reinforcement of training in pump use and diabetes as well as in trial procedures including the 4-point SMPG profiles, infusion set changes and completion of the diaries. Based on the Investigator's discretion after the run-in period, Subjects who have shown ability and willingness to adhere to the trial procedures and satisfactory handling of the pump will be randomised (Visit 6) in a 1:1 manner to NovoRapid® or faster-acting insulin aspart as described in section 11. After the 16-week treatment period, the Subject will have a 7-day follow-up (FU1, V 23) and 30-day (FU2, P 24) safety follow-up visit.

Up to 50% of the eligible Subjects will be allowed to wear their own real-time CGM device during the entire course of the trial. The remaining enrolled Subjects will not be allowed to wear a CGM device except for three pre-specified periods. During these periods a blinded CGM device will be

Protocol	Date:	04 February 2016	Novo Nordisk
Taia1 ID. NINI1210 2054	17	4.0	

Trial ID: NN1218-3854
UTN: U1111-1118-2480
EudraCT no.: 2010-024054-11

CONFIDENTIAL

CONFIDENTIAL

CONFIDENTIAL

Version:
Status:
Final
Page:
29 of 149

handed out to all Subjects by the Investigator (provided by Novo Nordisk), including Subjects wearing their own CGM.

5.2 Rationale for trial design

A 4-week run-in period has been included to ensure that the Subjects are being trained in the trial procedures and to collect 11 to 13 days baseline CGM measurements prior to randomisation.

A 16-week double-blinded, randomised treatment period is needed to obtain valid and adequate data regarding the effect and the safety. Treatment duration of 16 weeks is considered sufficient to reach a stable HbA_{1c} level in a CSII setting.

By including at least 50% of the Subjects without their own real-time CGM it will allow for assessing safety data in a population that does not have the possibility to look and react on real-time CGM data. The Subjects who enter the trial without their own real-time CGM device must not start wearing one when enrolled in the trial. The other 50% wearing an own GGM device are included to comply with the still-growing insulin pump population wearing a real-time CGM without changing their current normal practice when entering the trial. Subjects wearing their own CGM are not allowed to use the low glucose suspend mode in the relevant pumps during the trial in order to assess the safety profile of faster-acting insulin aspart. Randomisation will be stratified according to the use of own real-time CGM to ensure a comparable number of Subjects in each treatment group.

The rationale of the blinded CGM assessment is to obtain a thorough knowledge of the glycaemic control achieved with the different treatments in this trial.

The rationale for the meal test is to evaluate PPG excursions after a standardised meal when infusing faster-acting insulin aspart compared to NovoRapid[®].

A 7-day and 30-day follow-up visit is included in order to collect information on AEs occurring in the 30 days after discontinuation of trial drug.

The treat-to-target approach, and thereby the very high frequency of contacts, has been chosen in order to ensure optimal titration of faster-acting insulin aspart and NovoRapid[®].

This trial will be conducted at multiple centres to ensure that the required Subject population can be included.

5.2.1 Rational for choice of non-inferiority margin

Placebo controlled trials will usually be considered unethical to conduct in a T1DM diabetic population and it can therefore be difficult to assess the true insulin aspart effect. In a recently finalised faster-acting insulin aspart trial (NN1218-4049) in a bolus insulin naïve T2DM adult population comparing a basal insulin treatment in addition to metformin to a full basal bolus insulin

Protocol	Date:	04 February 2016	Novo Nordisk
Trial ID: NN1218-3854	 Version:	4.0	

 Trial ID: NN1218-3854
 CONFIDENTIAL
 Version: 4.0

 UTN: U1111-1118-2480
 Status: Final

 EudraCT no.: 2010-024054-11
 Page: 30 of 149

treatment in addition to metformin the estimated treatment difference in change from baseline HbA_{1c} was - 0.94%-point [-1.17; -0.72] (data on file). In that trial the addition of 3-times daily faster-acting insulin aspart lead to a reduction in HbA_{1c} of 1.16%-point after 18 weeks of treatment. In a similar phase 4 trial¹⁹ investigating the stepwise addition of NovoRapid[®] to a full basal bolus regimen in bolus naïve T2DM adults the observed reduction in HbA_{1c} after 21 weeks of treatment was 1.15%-point (data on file) with 3-times daily NovoRapid[®] added to basal insulin. This gives some indication that the effect of NovoRapid[®] versus placebo would be close to the 0.94%-point observed in trial NN1218-4049. Using a non-inferiority margin of 0.4, one of the suggested margins in the FDA guidance¹⁸, an improvement of approximately 0.54% would have been preserved using the 0.4% non-inferiority margin. It is also worthwhile to state that the T1DM population would not have any or limited endogenous insulin production and the true effect of NovoRapid[®] might be comparable to what is seen in a T2DM population.

5.3 Treatment of Subjects

At the start of the run-in period (Visit 2), Subjects will remain on their pre-trial insulin treatment. At randomisation (Visit 6), Subjects will be switched from their current insulin treatment to either faster-acting insulin aspart or NovoRapid[®] in a 1U:1U manner, keeping the current insulin delivery parameters in the pump. After the transfer to trial insulin treatment the insulin pump delivery parameters should be reviewed with regards to the need for adjustments. During the run-in period (Visit 2 to Visit 6), the basal rates and Bolus Wizard[®] should not be adjusted unless indicated for safety reasons.

In the treatment period starting at randomisation (Visit 6), the Investigators must strive to achieve a glycaemic target of fasting and pre-prandial BG between 4.0-6.0 mmol/L [71-108 mg/dL] in a treat-to-target fashion based on frequent SMPG profiles and safety. No maximum dose of insulin is specified. All Subjects will perform at least 4-point SMPG profiles on a daily basis, in accordance with section 8.3.2.2, throughout the trial. Guideline documents for the management of Insulin Pump Therapy will be provided both to the Investigators and the Subjects 20.21.

The dose adjustments must be done based on SMPG values only. No other anti-diabetic medication except the current insulin treatment is allowed during the trial after start of run-in period (Visit 2) until randomisation (Visit 6). No other insulin products except the trial medication are allowed from start of the randomisation (Visit 6) until end of treatment (Visit 22).

5.3.1 Basal rate insulin adjustment

The purpose of adjusting the basal rates is to ensure that BG is kept in a stable range within 2 mmol/L [35 mg/dL] in a fasting state and during the night. After randomisation (Visit 6), the Subjects should perform basal rate checks based on frequent measurements of SMPG values and the skipped meal principle, or similar, following instructions from the Investigator according to insulin adjustment guidelines for insulin pump users ^{20,21}.

Protocol		Date:	04 February 2016	Novo Nordisk
Trial ID: NN1218-3854	CONFIDENTIAL	Version:	4.0	

 Trial ID: NN1218-3854
 CONFIDENTIAL
 Version: 4.0

 UTN: U1111-1118-2480
 Status: Final Page: 31 of 149

During the treatment period, starting at randomisation (Visit 6), the Investigator must review and adjust if necessary the individual basal rates at each site and phone visit and inform the Subject accordingly. The Novo Nordisk insulin titration group will review the progress of treatment (please see section 5.4).

5.3.2 Bolus insulin titration

The Subjects should use meal-time boluses based on carbohydrate-counting using the Bolus Wizard® according to their usual practice and according to instructions from the Investigator. Meal-time dosing is defined as bolus infusion initiated 0-2 minutes before a meal. At randomisation (Visit 6), the individual BG target should be set in the pump to a mean of the upper and lower value in the target range and the Bolus Wizard® settings should be evaluated by the Investigator after basal rates checks or adjustments.

During the treatment period starting at randomisation (Visit 6), the Investigator must review and adjust if necessary the insulin to carbohydrate ratios and correction factors at each site and phone visit according to insulin adjustment guidelines for pump users^{20,21}, and advise the Subject accordingly. The Investigator should also review correction boluses and adjust the active insulin setting in case of any signs of incorrect settings. The Subject must be informed not to change the active insulin setting without discussing this with the Investigator. The Novo Nordisk insulin titration group will review the progress of treatment.

5.4 Titration review procedure

Surveillance of titration data will be performed centrally by Novo Nordisk in a blinded manner. During the trial HbA_{1c} will be monitored by Novo Nordisk for additional surveillance of the glycaemic control. Novo Nordisk will be in contact with sites (visit or phone contact) to discuss progress in glycaemic control and titration of individual Subjects based on SMPGs and HbA_{1c} . This will be done in a blinded manner. When the Investigator receives an inquiry, a response should be received at Novo Nordisk within 24 hours (on weekdays).

5.5 Treatment after end of trial product

When discontinuing trial products, either at end of treatment (Visit 22) or earlier, the Subject should be switched to a suitable marketed product at the discretion of the Investigator. Please see section 8.1.9.

5.6 Rationale for treatment

CSII treatment of adult patients with T1DM was introduced more than 30 years ago and found to generate improvements with respect to glucose control. Data from the DCCT show that intensive treatment is beneficial in terms of reducing the risk for long term complications³.

Protocol		Date:	04 February 2016	Novo Nordisk
Trial ID: NN1218-3854	CONFIDENTIAL	Version:	4.0	
UTN: U1111-1118-2480	CONFIDENTIAL	Status:	Final	
EudraCT no.: 2010-024054-11		Page:	32 of 149	

The currently available clinical pharmacology data demonstrates that injection with faster-acting insulin aspart formulations results in an increased early absorption of insulin aspart compared to NovoRapid[®] and thereby provides a faster onset of insulin action.

A delay between the glucose measurements and the insulin absorption (so called lag-time) due to the s.c. route of insulin delivery can limit the possibility of reducing the excessive PPG excursions. The rapid action of faster-acting insulin aspart could prove more effective in achieving PPG control in a CSII regimen because of the shortened absorption time of faster-acting insulin aspart from the s.c. depot at the infusion site.

NovoRapid[®] will be applied as a comparator to faster-acting insulin aspart in order to compare and confirm clinical effect and safety of faster-acting insulin aspart to the currently marketed insulin aspart formulation NovoRapid[®]. As the trial is double-blinded, faster-acting insulin aspart and NovoRapid[®] will be titrated following the same recommendations.

Protocol Date: 04 February 2016 Novo Nordisk
Trial ID: NN1218-3854 Version: 4.0

 Trial ID: NN1218-3854
 CONFIDENTIAL
 Version: 4.0

 UTN: U1111-1118-2480
 Status: Final

 EudraCT no.: 2010-024054-11
 Page: 33 of 149

6 Trial population

6.1 Number of Subjects

Number of Subjects planned to be screened: 666

Number of Subjects planned to be included in the run-in period: 506

Number of Subjects planned to be randomised: 450

Approximately a 24% screening failure rate and 11% run-in failure rate are expected for this trial.

6.2 Inclusion criteria

For an eligible Subject, all inclusion criteria must be answered "Yes".

- 1. Informed consent obtained before any trial-related activities. Trial-related activities are any procedures that are carried out as part of the trial, including activities to determine suitability for the trial
- 2. Male or female, age ≥ 18 years at the time of signing informed consent
- 3. Diagnosed with T1DM \geq 1 year prior to the day of screening
- 4. Using the same Medtronic pump (Minimed 530G (551/751), Paradigm Veo (554/754), Paradigm Revel (523/723), Paradigm (522/722)) for CSII in a basal-bolus regimen with a rapid acting insulin analogue for at least six months prior to screening and willing to stay on the same pump model throughout the trial (if the model is changed the change should not exceed 7 consecutive days.)
- 5. Ability and willingness to refrain from using low glucose suspend mode in the pump throughout the trial
- 6. Willingness to use one of the following types of infusion sets: Medtronic Quick-Set[®], Medtronic Mio[®], Medtronic Silhouette[®] or Medtronic Sure-T[®] (Easy-set[®]) throughout the trial
- 7. Willing to use CSII as the insulin treatment during the entire trial
- 8. Using the same insulin for at least 90 days prior to screening
- 9. HbA_{1c} 7.0-9.0% (53-75 mmol/mol) inclusive as assessed by central laboratory at screening
- 10. BMI \leq 35.0 kg/m² at screening

Protocol	Date:	04 February 2016	Novo Nordisk
Trial ID: NN1218-3854	Version:	4.0	

 Trial ID: NN1218-3854
 CONFIDENTIAL
 Version: 4.0

 UTN: U1111-1118-2480
 Status: Final

 EudraCT no.: 2010-024054-11
 Page: 34 of 149

11. Ability and willingness to take at least 3 daily meal-time insulin bolus infusions every day throughout the trial

12. Ability and willingness to adhere to the protocol including performing SMPG profiles, CGM and meal test

6.3 Exclusion criteria

For an eligible Subject, all exclusion criteria must be answered "No".

- 1. Known or suspected hypersensitivity to trial products or related products
- 2. Previous participation in this trial. Participation is defined as signed informed consent
- 3. Female who is pregnant, breast-feeding or intends to become pregnant or is of child-bearing potential and not using adequate contraceptive methods (adequate contraceptive measures as required by local regulation or practice)

For UK: Females of child-bearing potential who are pregnant, breast-feeding or intend to become pregnant and are sexually active and not using adequate contraceptive methods (Adequate contraceptive measures are defined as established use of oral, intravaginal, transdermal combined estrogen and progestogen hormonal methods of contraception; oral, injected or implanted progestogen only hormonal methods of contraception; placement of an intrauterine device or intrauterine hormone releasing system, bilateral tubal occlusion, barrier methods of contraception (condom or occlusive cap with spermicidal foam/gel/film/cream/suppository), female sterilisation, vasectomised partner (where partner is sole partner of Subject), or true abstinence (when in line with preferred and usual lifestyle))

For Belgium: Highly effective methods of birth control are defined as those, alone or in combination, that result in a low failure rate (i.e., less than 1% per year) when used consistently and correctly; such as implants, injectables, combined oral contraceptives, some IUDs, true sexual abstinence (i.e. refraining from heterosexual intercourse during the entire period of risk associated with the study treatments) or vasectomised partner.

For Germany: Adequate contraceptive measures are defined as implants, injectables, combined oral contraceptives, hormonal intrauterine device and sexual abstinence or vasectomised partner.

4. Participation in another clinical trial within 28 days before the screening visit. Participation is defined as having signed SI/IC. Note: clinical trials do not include non-interventional studies

Protocol	Date:	04 February 2016	Novo Nordisk
Tain 1 ID. MNI1010 2054	Margian.	4.0	

 Trial ID: NN1218-3854
 Version:
 4.0

 UTN: U1111-1118-2480
 Status:
 Final

 EudraCT no.: 2010-024054-11
 Page:
 35 of 149

5. Anticipated significant change in lifestyle (e.g. eating, exercise or sleeping pattern) throughout the trial

- 6. Any of the following: myocardial infarction, stroke, hospitalization for unstable angina or transient ischaemic attack within the past 180 days prior to the day of screening
- 7. Subjects classified as being in New York Heart Association²² (NYHA) Class IV at screening
- 8. Planned coronary, carotid or peripheral artery revascularisation known on the day of screening.
- 9. Inadequately treated blood pressure defined as Grade 3 hypertension or higher (Systolic ≥180 mmHg or diastolic ≥110 mmHg) at screening
- 10. Impaired liver function, defined as ALT \geq 2.5 times upper normal limit at screening
- 11. Renal impairment measured as estimated Glomerular Filtration Rate (eGFR) value of eGFR < 60 ml/min/1.73 m² as defined by KDIGO 2012 classification using isotope dilution mass spectrometry (IDMS) for serum creatinine measured at screening. (KDIGO 2012²³)
- 12. Anticipated initiation or change in concomitant medications (for more than 14 consecutive days) known to affect weight or glucose metabolism (e.g. treatment with orlistat, thyroid hormones, or corticosteroids)
- 13. Proliferative retinopathy or maculopathy requiring acute treatment as verified by fundus photography or dilated fundoscopy performed within 90 days prior to the screening visit or as part of the screening assessments. Results must be present at Visit 2.
- 14. History of hospitalization for ketoacidosis ≤180 days prior to the day of screening
- 15. Treatment with any medication for the indication of diabetes or obesity other than stated in the inclusion criteria within 90 days before screening
- 16. Presence or history of malignant neoplasms within the past 5 years prior to the day of screening. Basal and squamous cell skin cancer and any carcinoma in-situ is allowed.
- 17. Any condition which, in the opinion of the Investigator might jeopardise Subject's safety or compliance with the protocol
- 18. Intention to start using a flash glucose monitoring or real-time CGM system device for personal use at any time after screening until the end of trial

 Trial ID: NN1218-3854
 CONFIDENTIAL
 Version: 4.0

 UTN: U1111-1118-2480
 Status: Final

 EudraCT no.: 2010-024054-11
 Page: 36 of 149

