6.4 Run-in failure criteria

Subjects fulfilling any of the below listed criteria or withdrawing consent prior to randomisation are considered run-in failures and should follow the procedures described in section 8.1.3.1.

- 1. Included in the trial in violation of the inclusion and/or exclusion criteria
- 2. Pregnancy
- 3. Intention of becoming pregnant
- 4. Participation in other clinical trials throughout the trial. Participation is defined as signed informed consent (note; clinical trials do not include non-interventional studies)

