8.2.4 Childbearing potential

It must be recorded in the eCRF whether female Subjects are of childbearing potential.

Female of non-childbearing potential is defined as, but not limited to:

- A female who has undergone a hysterectomy, bilateral oophorectomy or bilateral tubal ligation
- Postmenopausal defined as no menses for 12 months without an alternative medical cause
- Other medical reasons preventing childbearing potential

Pregnancy testing must be performed on females with childbearing potential, as described in Section 8.4.7.

The Subjects must be instructed to use contraceptive methods, as described in Exclusion Criterion number 3, throughout the trial and until 1 week after end of treatment.

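### Exclusion criterion 3: the UK paragraph and the general text give different answers on missing contraception and on intended pregnancy, and the protocol does not say which governs

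*Protocol*

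**What the plan says.** Protocol section 6.3 allows enrolment only if every exclusion criterion is answered in the negative. The general text of criterion 3 lists four separate grounds: "Female who is pregnant, breast-feeding or intends to become pregnant or is of child-bearing potential and not using adequate contraceptive methods". A parenthesis leaves one matter to the country: "adequate contraceptive measures as required by local regulation or practice".

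Three country paragraphs follow. Those for Belgium and Germany only describe acceptable methods. The UK paragraph also has a list of methods, which includes true abstinence, but it first restates the criterion, for women of child-bearing potential "who are pregnant, breast-feeding or intend to become pregnant and are sexually active and not using adequate contraceptive methods".

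Other sections that bear on the point:

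- Section 6.4 (run-in failure) and section 6.6.1 (mandatory discontinuation of trial product) each list pregnancy and, separately and without further condition, "Intention of becoming pregnant". Each also lists inclusion in violation of the eligibility criteria. Neither lists missing contraception.
- Section 8.2.4: "The Subjects must be instructed to use contraceptive methods, as described in Exclusion Criterion number 3, throughout the trial", and for one week after treatment ends.
- Protocol section 17.2 and SAP section 2.2 remove from the per protocol (PP) set anyone who fulfilled an exclusion criterion.

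**The concern.** In the general text the contraception condition is a ground of its own, introduced by *or*. In the UK paragraph it is introduced by *and*, so it reads as a qualifier on the items before it. The woman whom a contraception condition most plainly addresses (sexually active, unprotected, no wish for pregnancy) meets the general text but not the UK one. Intention also becomes conditional in the UK paragraph, which does not fit sections 6.4 and 6.6.1.

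Two things are at stake. One is consistent application of a safety-related eligibility rule at UK sites. The other is classification. If the UK paragraph is applied at entry and the general text later, the same woman becomes a violation. That means run-in failure before randomisation, or mandatory discontinuation and loss from the PP set after it.

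**Working it through.** The plan gives no figure to reproduce, so the check is one of logic.

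**Inputs.** For a woman of child-bearing potential, take five yes/no attributes: P pregnant, B breast-feeding, I intends pregnancy, S sexually active, C uses adequate contraception. That gives 2^5 = 32 profiles. These are logical combinations, not frequencies.

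**Rules as written**

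- General text: P or B or I or not C. Only P = B = I = no with C = yes escapes, with S free: 2 profiles. Excluded: 32 − 2 = 30.
- UK, *and* governing the whole list: (P or B or I) and S and not C. There are 7 combinations of P, B, I with at least one yes, and one setting of S and C. Excluded: 7.
- UK, *and* governing only the last item: P or B or (I and S and not C). P or B holds in 3 × 8 = 24 profiles, plus one with P = B = no. Excluded: 25.

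Every profile excluded under either UK grouping is also excluded by the general text. The UK paragraph is therefore strictly narrower, by 30 − 7 = 23 or 30 − 25 = 5 profiles.

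**Profiles that matter**

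| Woman of child-bearing potential | General | UK, *and* on whole list | UK, *and* on last item |
|---|---|---|---|
| Sexually active, no contraception; not pregnant, not breast-feeding, no intention | excluded | not excluded | not excluded |
| Intends pregnancy, uses contraception; not pregnant, not breast-feeding | excluded | not excluded | not excluded |
| Breast-feeding, uses contraception | excluded | not excluded | excluded |
| Pregnant, not sexually active | excluded | not excluded | excluded |

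The first two rows do not depend on the grouping. The last two do.

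**Does another rule close the gap?** Sections 6.4 and 6.6.1 catch pregnancy and intention, but not missing contraception or breast-feeding. Section 8.2.4 is an instruction that refers back to criterion 3, not an entry bar. The pregnancy tests in the flow chart (Visits 1, 6, 22 and 22A) and in section 8.4.7 detect pregnancy and say nothing about contraception. Exclusion criterion 17 is investigator discretion. The September 2016 amendment text in the documents leaves criterion 3 unchanged.

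**Consequence for classification.** Take the woman in the first row, enrolled under the UK paragraph. If the general text governs, she was included in violation. Section 6.4 item 1 or section 6.6.1 item 1 then applies, and she leaves the PP set used in sensitivity analysis 7 (protocol 17.3, SAP 2.3). If the UK paragraph governs, none of this follows. She stays in the full analysis set either way, apart from the exceptional exclusions that section 17.2 allows.

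**The case against.** The strongest objection is that nothing says the UK paragraph replaces the general text. The general text carries no country limit, all criteria must be answered in the negative, and its parenthesis invites local detail. If the country paragraphs only supplement it, the unprotected UK woman is still excluded. This stands. A reader might infer that UK sites are shown to admit such women; the documents do not support that. They show two texts with different answers and no rule of precedence. A complete restatement headed for the UK is, however, naturally read as the operative text there.

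A second objection is that *and* may simply add a category: women who are pregnant, breast-feeding or intending pregnancy, and also those who are sexually active and unprotected. The attached list of methods fits that intent. Coded as P or B or I or (S and not C), this excludes 7 × 4 + 1 = 29 profiles. It differs from the general text in one: no contraception and not sexually active, which the UK allowance for true abstinence largely covers. This may be what was meant, but the grammar has to be strained to get there, and an eligibility rule should not need that.

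Third, there are safeguards: the section 8.2.4 instruction, the pregnancy tests, and the pregnancy and intention criteria. They limit the harm and stand as mitigation, but they do not make the two texts agree.

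Fourth, a reader might try to put a number on women at risk. Assuming 5–15% of the 450 randomised are in the UK and 30% of those are women of child-bearing potential gives 450 × 0.05 × 0.30 = 6.75 to 450 × 0.15 × 0.30 = 20.25, about 7 to 20. Neither share is in the documents. The product also counts everyone the paragraph would govern, not those for whom the two texts differ, a subset that could be empty. It should not be used as an estimate of the effect.

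**Conclusion.** The contradiction is real and is visible within one criterion. Under both natural groupings of the *and*, the UK paragraph fails to capture a sexually active, unprotected woman with no wish for pregnancy, whom the general text excludes. It also makes intention conditional where sections 6.4 and 6.6.1 do not. Because precedence is unstated, eligibility and violation status can differ for the same woman.

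The reach is limited. It concerns UK women of child-bearing potential for whom the two texts differ; their number cannot be derived from the documents and may be very small or zero. Sample size, power and type I error are unaffected, and the PP set enters only a sensitivity analysis. The conclusion rests on reading the UK sentence literally. A reader might also infer that the general text must be the right rule and the UK one an error. The documents do not show where the UK wording came from, so they support a call for reconciliation, not a choice between the two. It should be corrected, but it does not threaten the primary conclusion.

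**What to change.** In a UK-specific amendment, reconcile the two texts of criterion 3 so that they give one answer for every woman, and align the treatment of intention with sections 6.4 and 6.6.1. State once in section 6.3 whether country paragraphs replace the general criterion or only supplement it.

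One drafting route that fits the protocol's own structure is to limit the UK paragraph to its definition of adequate measures, as the German paragraph does, subject to confirmation by the sponsor and the UK regulator. The Belgian paragraph needs a smaller tidy-up: it defines a term that the general criterion does not use, and the link should be made explicit.

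If UK subjects are already enrolled, record before database lock which text was applied at entry, so that violation status and PP membership are settled while blinded.

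The cost is a change of a clause or so, one added sentence and the usual amendment approvals. No analysis, sample size or timeline changes.
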